3.9 Period of Observation

After completion of study drug, subjects will enter follow-up and will be contacted regularly by the Investigator or study personnel to collect information about subsequent therapies, disease status, and survival. Subjects will be followed for safety, duration of response (DOR), progression free survival (PFS), and overall survival (OS) until the end of the study, (see below).

Observation Visits:

- End of Treatment visit: Visit to be performed 14 days (± 2 days) from last drug intake or before start of any new anti-cancer treatment whichever is sooner. For subjects who discontinue prematurely before disease progression it must be performed as the last visit.
- Safety Follow Up visit: All subjects will undergo one Safety Follow-up visit 30 days (± 5 days) after the last AFM24 infusion or before start of any new anti-cancer treatment whichever is sooner.
- Long-term Follow Up: Additional follow-up (phone contact) will take place at 3-month intervals (± 2 weeks) after end of treatment visit until death, lost to follow-up- or mutual decision between PI and sponsor to discontinue Long-term Follow Up of the patient, whichever is sooner.
- End of Study: The study will be terminated as soon as all subjects have completed the first Long-term Follow-Up interval, withdrawn, or died, whichever occurs first.

The study will be analyzed and reported once the last subject of the study has experienced at least one of the following:

- Has been treated till at least 4 weeks after the 1st post-baseline tumor assessment
- Disease progression
- Withdrawal from treatment due to a drug related AE
- Fatal event
- Lost to Long-term Follow-Up
- Withdrawal of consent
- Start of other anti-cancer treatment

In case subjects are still being treated with study medication at the primary analysis cut-off date for this study, such subjects will be kept on treatment in the study and data collected will then be reported in an addendum to the final clinical study report (CSR). It will be noted in the final CSR that such a revised report may be provided.

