5.2 Study Drug Administration

All doses of AFM24 will be administered as an i.v. infusion. During the dose escalation phase (Phase 1), subjects will receive AFM24 as a weekly infusion. As mentioned in Section 3.1, additional dosing regimen (i.e., q2w) may be explored in the dose expansion phase (Phase 2a) **only**.

For dose escalation phase (Phase 1) and dose expansion phase (Phase 2a)

- Weekly dosing regimen (q1w): i.e., on Day 1, Day 8, Day 15, and Day 22 of a 28-day cycle (see APPENDIX A [Section 14.1]).

For dose expansion phase (Phase 2a) only

In addition to the weekly dosing regimen mentioned above, the following dosing regimen may be used:

- Every-2-weeks dosing regimen (q2w): i.e., on Day 1 and Day 15 of a 28-day cycle (see APPENDIX B [Section 14.2]). If the drug is given on a q2w schedule, the daily dose will not be higher than the highest daily dose that was tested in Phase 1 part of the study and was considered safe.

The baseline infusion time should not take less than approximately 4 hours for at least the first 2 AFM24 infusions (**Note:** infusion time is approximately 4 hours, any infusion time \geq 3 hour 50 minutes will not be a deviation). It should also be noted that as the dose escalation continues into the higher dosing cohorts, the baseline infusion time may increase to >4 hours and as long as over 2 days (ie, split day dosing) based on a given subject's tolerability as detailed in the Pharmacy Manual for each cohort. For infusion times that span over 2 days (i.e., split day dosing), timepoints for different assessment may be affected and the Schedule of Assessment (SoA) tables should be referenced for details (See Section 14.1 and Section 14.2 for SoA tables

for weekly and q2w dosing schedules, respectively). If the first 2 consecutive AFM24 infusions are well tolerated (defined as no IRR/cytokine release syndrome (CRS) Grade >1), then the infusion time may be decreased to <4 hours to a minimum of 1 hour starting with the third subsequent infusion (ie, C1D15 for weekly dosing regimen and C2D1 for q2w dosing regimen) at the discretion of the Investigator along with a potential reduction of post infusion- observation period (with regular checks of vital signs, please refer to [Table 5](#) for detailed description) from 4 hours to a minimum of 2 hours and a taper of corticosteroid premedication. Investigators should only make 1 modification per infusion at 1 time.

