9.3.4.2 Phase 2a (Dose Expansion)

Once the MTD and/or at least one RP2D is determined, enrollment of subjects into 1 of several expansion cohorts for selected tumor indications may begin at the RP2D. The SRC may select an RP2D that is below the MTD, or if an MTD is not reached, an RP2D may be selected by the SRC after careful review of all available clinical and laboratory data from Phase 1. The RP2D will not exceed the MTD.

The primary objective of the expansion phase is to determine preliminary efficacy as objective response (OR) using a Simon's two-stage design. The primary endpoint is based on the objective response assessed by local Investigator according to RECIST v1.1 (Eisenhauer et al., 2009; Schwartz et al., 2016). The primary analysis will take place once all subjects per cohort had at least 1 confirmed response assessment (ie, ≥ 12 weeks post-baseline) or have been withdrawn from the study.

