- o. Urinalysis parameters include glucose, protein, bilirubin, ketones, blood, pH, specific gravity (microscopic examination when indicated), FSH (to confirm post-menopausal status [Screening], and human chorionic gonadotropin (female pre-menopausal subjects [Screening] (See [APPENDIX D](#), Section [14.4](#)).
- p. Coagulation may be assessed from the hematology sample.

- q. Tumor biopsy for central analysis is required for subjects in the dose escalation phase (Phase 1) only.
- r. +1 week: The second tumor biopsy will be performed on a non-dosing day during week 3 (+1 week).
- s. CT or MRI will be done at Screening and during the last week of cycles 2, 4, 6, 8, and every 3 cycles thereafter.
- t. During pre-screening, only AEs which are related to study procedures are to be recorded. AEs occurring after signing of the Main ICF but prior to the first dose of study drug should be recorded on the Medical History eCRF page (**Note:** any SAEs which are related to study procedures and occur during pre-screening and any SAEs that occur following signing the Main ICF and prior to the first dose of study drug will still be reported using the SAE form). Please also refer to Section 8.1.3 for detailed description.
- u. Concomitant medications administered after the Safety Follow-up visit should be recorded for SAEs which are considered related to study drug.

ADA = anti-drug antibodies; C = cycle; CT = computed tomography; ctDNA = circulating tumor DNA; D = day; ECG = electrocardiogram; ECOG PS = Eastern Cooperative Oncology Group Performance Status; EGFR = epidermal growth factor receptor; EOI = end of infusion; EOT = End of Treatment visit; FSH = follicle-stimulating hormone; HIV = human immunodeficiency virus; I/E = inclusion/exclusion; ICF = informed consent form; LT-FU = long term follow-up; MRI = magnetic resonance imaging; PD = pharmacodynamics; PK = pharmacokinetics; SCR = screening; S-FU = Safety Follow-up visit.

Table 12: Schedule of Pharmacokinetic, Pharmacodynamic, Immunogenicity, and Translational Assessments for Weekly AFM24 Dosing Regimen (Without Split Dosing) - For Phase 1

Sample	SCR	Cycle 1												
		D1			D3		D7	D8	D15	D22			D24	D28
		Pre	EOI ^a	+1h EOI ^a	+48h EOI ^a	+2h	+144h EOI ^a	Pre	Pre	Pre	EOI ^a	+1h EOI ^a	+48h EOI ^a	+144h EOI ^a
PK		X	X		X	X	X	X	X	X	X	X	X	X
ADA ^b		X					X	X	X					
CD16a RO	X				X					X			X	
PD (circulating lymphocytes)		X		X	X			X	X	X		X	X	
PD (cytokines) ^c		X	X		X			X	X	X	X		X	

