- m. Urinalysis parameters include glucose, protein, bilirubin, ketones, blood, pH, specific gravity (microscopic examination when indicated), FSH (to confirm post-menopausal status [Screening], and human chorionic gonadotropin (female pre-menopausal subjects [Screening] (See APPENDIX D, Section 14.4)).
- n. Coagulation may be assessed from the hematology sample.
- o. CT or MRI will be done every 8 weeks after baseline assessment for first 4 assessments, and every 12 weeks thereafter.
- p. Concomitant medications administered after the Safety Follow-up visit should be recorded for SAEs which are considered related to study drug.
- q. Only taken in Cycle 2 at sites that can perform the PBMC isolation according to the lab manual/Sponsor requirements.
- r. During pre-screening, only AEs that are related to study procedures are to be recorded. AEs occurring after signing of the Main ICF but prior to the first dose of study drug should be recorded on the Medical History eCRF page (**Note:** any SAEs that are related to study procedures and occur during pre-screening and any SAEs that occur following signing the Main ICF and prior to the first dose of study drug will still be reported using the SAE form). Please also refer to Section 8.1.3 for detailed description.

ADA = anti-drug antibodies; C = cycle; CT = computed tomography; ctDNA = circulating tumor DNA; D = day; ECG = electrocardiogram; ECOG PS = Eastern Cooperative Oncology Group Performance Status; EGFR = epidermal growth factor receptor; EOI = end of infusion; EOT = End of Treatment visit; FSH = follicle-stimulating hormone; HIV = human immunodeficiency virus; I/E = inclusion/exclusion; ICF = informed consent form; LT-FU = long term follow-up; MRI = magnetic resonance imaging; PD = pharmacodynamics; PK = pharmacokinetics; SCR = screening visit; S-FU = Safety Follow-up visit.

Table 17: Schedule of Pharmacokinetic, Pharmacodynamic, Immunogenicity, and Translational Assessments for Every 2 Weeks AFM24 Dosing Regimen (Without Split) - Phase 2a Only

Samples	Cycle 1							Cycle 2							Subsequent Cycles		EOT ^f
	D1				D3	D15	D1+1					D3+1	D15±1	D1+1			
	Pre	+2h SoI	+4h ^a SoI	EOI ^b	+48 h EOI		Pre	Pre	+2h SoI±15 min	+4h ^a SoI±15 min	EOI ^b	+48h EOI		Pre	Pre	±2 days	
	-2h max	±15 min	±15 min	+15 min	±2h		-2h max	-2h max	SoI±15 min	SoI±15 min	+15 min	±2h		-2h max	-2h max		
PK	X			X	X	X	X	X			X	X	X	X	X	X	
ADA ^c	X						X	X						X	X	X	
PD (circulating lymphocytes) ^d	X			X	X		X	X			X	X		X			

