Primary endpoint for this phase will be Overall response rate (complete response [CR] + partial response [PR]) assessed by local RECIST v1.1. Best confirmed overall response will be used to define the ORR. The table below summarizes the confirmation rules:

Response at first visit	Response at consecutive visit (at least 4 weeks after the initial assessment)	Confirmed Response at visit
CR	CR	CR
CR	PR	PD
CR	SD	SD*
CR	PD	PD
PR	CR	PR
PR	PR	PR
PR	SD	SD*
PR	PD	PD
SD	CR	SD*

CONFIDENTIAL

Page 15 of 22

Statistical Analysis Plan template version 1.0 dated 27-MAR-2019

SD	PR	SD*
SD	SD	SD*
SD	PD	PD

CR = complete response; PD = progressive disease; PR = partial response; SD = stable disease

* - In order to assign Stable Disease as a confirmed response, there has to be another assessment of at least SD no less than 7 weeks after the initial visit. If this criterion is not satisfied, assign PD.

If the closest consecutive visit is closer than 4 weeks, or is not evaluable, use the next available assessment for confirmation. The last visit has no confirmed response. For iRECIST data similar approach will be used to define the confirmed response at visit.

Simon's two-stage design will be used to determine the outcome of the study in each of the three cohorts. The table below shows the decision thresholds for the design for all three cohorts:

Indication	Interim Analysis		Final Analysis	
	Number of subjects	OR, that may lead to stop	Number of subjects*	OR (rejection of the null hypothesis)
RAS-wt, microsatellite stable CRC	11	≤1	39	≥4
ccRCC	15	≤2	41	≥10
NSCLC EGFRmut	15	≤2	41	≥10

CRC = colorectal cancer; EGFRmut = epidermal growth factor receptor mutant; RAS-wt = rat sarcoma genes-wild type; NSCLC = non-small cell lung cancer; OR = objective response

*Up to a total of N~40 subjects per Cohort

The final analysis will take place after the last expansion arm was closed for futility or the last patient of the last expansion arm had the final end-of-study visit. Summaries will include the count and percentages of different best confirmed overall responses for each cancer type and observed ORR. In the final analysis, a p-value using the exact binomial test will be calculated comparing the response proportion to the probability stated under H_0 for each indication separately.

Listing of CT scan data, reporting both confirmed and unconfirmed responses at all visits will be created. Additionally, biopsy data will be listed.

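### Protocol 3.9, Protocol 9.3.4.2 and SAP 7.7.1 give conflicting triggers for the final Phase 2a analysis, and two of them do not wait for the scan that could confirm a response

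*Protocol*

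**What the plan says.** Three places set the timing of the Phase 2a analysis.

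- **Protocol 9.3.4.2:** "The primary analysis will take place once all subjects per cohort had at least 1 confirmed response assessment". The section glosses this as 12 weeks or more after baseline and lets withdrawal stand in for it. Protocol 10.4 ties the clinical study report to this section.
- **Protocol 3.9:** "The study will be analyzed and reported once the last subject of the study has experienced at least one of the following". The first item is "Has been treated till at least 4 weeks after the 1st post-baseline tumor assessment". The others are progression, withdrawal for a drug-related adverse event, death, loss to follow-up, withdrawal of consent and new anticancer treatment. The first item asks for time on treatment, not for a second scan.
- **SAP 7.7.1:** "The final analysis will take place after the last expansion arm was closed for futility". The alternative is the final end-of-study visit of the last patient in the last arm. The futility branch has no minimum follow-up.

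The scan schedule on weekly dosing (Protocol Appendix A, Table 11, note s) is: "CT or MRI will be done at Screening and during the last week of cycles 2, 4, 6, 8, and every 3 cycles thereafter". On every-2-weeks dosing (Appendix B, Table 16, note o) it is: "CT or MRI will be done every 8 weeks after baseline assessment for first 4 assessments, and every 12 weeks thereafter". Neither table contains a separate confirmation scan.

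Protocol 7.2.11 requires a CR or PR to be confirmed by a repeat assessment 4 weeks or more later. SAP 7.7.1 bases the ORR on best confirmed response and adds: "The last visit has no confirmed response". SAP 8 keeps recruitment open until an interim is complete.

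**The concern.** A confirmed response needs two scans. A trigger that can be met after one scan, or after none, allows the primary endpoint to be analysed before it can be observed in the last subjects enrolled. Under the SAP rule, a subject whose only scan shows a PR has no confirmed response.

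The exposed subjects are those enrolled late, including any who joined a cohort while its interim was under way. Protocol 3.8 and 9.3.8.2 report that Cohorts A and C were stopped for futility and that Cohort B enrolment was then ended at 8 patients, so the early-closure route is not remote. At stake are the reported ORR, the exact binomial p-value that SAP 7.7.1 attaches to it, and the possibility that one dataset yields different ORRs depending on which trigger is followed.

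**Working it through.** **Inputs.** The cycle length is 28 days, with doses on "Day 1, Day 8, Day 15, and Day 22 of a 28-day cycle" (Protocol 5.2). Scan weeks come from Appendices A and B, and the 4-week confirmation interval from 7.2.11. C1D1 is day 1.

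**Step 1: scheduled scans, weekly regimen.** The last week of Cycle k runs from day 28(k − 1) + 22 to day 28k.
- Cycle 2: 28 × 1 + 22 = day 50, to day 56.
- Cycle 4: 28 × 3 + 22 = day 106, to day 112 (weeks 15.1 to 16.0).
- Cycle 6: 28 × 5 + 22 = day 162, to day 168.

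**Step 2: the plan's own figure.** A first scan at week 8 plus 4 weeks gives week 12. The 12-week figure in 9.3.4.2 and 9.3.8.2 is therefore reproduced as the earliest time a first-scan response could be confirmed. It is not the date of the second scheduled scan.

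**Step 3: the 3.9 condition.** 50 + 28 = day 78, and 56 + 28 = day 84.

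**Step 4: gap to the second scheduled scan.** The shortest is 106 − 84 = 22 days and the longest is 112 − 78 = 34 days. It is 28 days if both scans fall on the same day of their week.

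**Step 5: every-2-weeks regimen.** Scans fall 8 and 16 weeks after the baseline assessment. The 3.9 condition is met at 8 + 4 = 12 weeks, so the gap is 4 weeks. Protocol 3.2 allows the baseline scan up to 28 days before first dose, so the second scan lies between 16 − 4 = 12 and 16 weeks after first dose. A rule written only as the Cycle 4 scan would not fit this regimen.

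**Step 6: the SAP futility branch.** It has no follow-up term, so no gap can be computed. The documents give no enrolment or closure dates.

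**Step 7: size of one reclassified subject (1/N).**
- Cohort B, N = 8: 1/8 = 12.5 points.
- Cohort A: the final size is not given. The 11 interim subjects are covered by 9.3.8.2, so an exposed subject implies N of at least 12. The range is 1/12 = 8.3 points down to 1/39 = 2.6 points.
- Cohort C: likewise, N of at least 16. The range is 1/16 = 6.3 points down to 1/41 = 2.4 points.

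**The case against.** The strongest reply is that 9.3.4.2 already controls the Phase 2a primary analysis. It waits for a confirmed response assessment, and 10.4 ties the report to it. Twelve weeks is stated as a minimum, which a scan at weeks 15-16 satisfies. This stands. Read strictly, 9.3.4.2 protects the endpoint, and the 12-week gloss is not a wrong date. But 3.9 and SAP 7.7.1 say something else, and neither document says which prevails. If the gloss is read as elapsed time alone, 9.3.4.2 has the same gap.

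Several stronger readings are tempting but not supported:
- **That late responders are in fact lost.** Protocol 7.2.11 does not require the repeat assessment to be a scheduled one, and 7.2 permits extra assessments on clinical grounds. A repeat scan around week 12 would confirm a first-scan response.
- **That a response first seen at Cycle 4 must wait for Cycle 6.** That holds for scheduled scans only. An unscheduled scan from about week 20 would suffice.
- **That one subject is worth 1/11 or 1/15 in Cohorts A and C.** Those are the interim sets, for which 9.3.8.2 and SAP 8 already require the confirming assessment or withdrawal.
- **That the SAP futility clause has been triggered for Cohort B.** The protocol describes an early end to enrolment without a Cohort B interim. The SAP, written to protocol version 9.0, still plans that cohort to 41. Whether this counts as closure for futility is undefined.

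Two further points limit the consequences. With 8 subjects, Cohort B cannot reach the 10 responses needed for rejection, so no Simon decision changes there. Also, 3.9 and 10.4 send later data to a report addendum, but only for subjects still on treatment, and neither section says that the final ORR will be revised.

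**Conclusion.** The conflict between the triggers is real and should be resolved. The 3.9 condition can be met 22 to 34 days before the second scheduled scan on weekly dosing, and the SAP futility branch has no follow-up floor.

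Downward bias in the ORR is possible rather than demonstrated. It requires that 3.9 or the SAP futility clause governs, that a late subject responds, and that no unscheduled confirmatory scan is done. It also assumes that an unconfirmed subject stays in the safety-set denominator named in SAP 7.7. The SAP 7.1 default of using non-missing values leaves that slightly open.

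Under these conditions one subject costs 12.5 points in Cohort B. For Cohorts A and C only the ranges above can be given. With the safety-set denominator the error cannot produce a false positive. It would understate activity in the reported estimate.

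**What to change.** Use one trigger in Protocol 3.9, Protocol 9.3.4.2 (with its synopsis copy) and SAP 7.7.1. Every treated subject must meet at least one of these conditions:

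- has had the second scheduled post-baseline scan for their regimen (last week of Cycle 4 on weekly dosing; the second 8-weekly scan on every-2-weeks dosing);
- has had a repeat scan at least 4 weeks after a first CR or PR;
- has progressed, died, withdrawn or started new anticancer therapy.

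Make the SAP futility-closure clause subject to this condition. State that 12 weeks is the earliest confirmation time and does not replace the second scan.

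The cost is wording in two documents and a data cut about 4 weeks later for the last subjects. No extra patients are needed. Holding the cut open for a response first seen at the latest scan is optional. For one first seen at the second scan, that would mean waiting to about week 20 with an unscheduled scan, or to days 162-168 on the weekly schedule.

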3.10 Number of Subjects

The study will enroll subjects with advanced or metastatic solid malignancies whose disease has progressed after treatment with previous anticancer therapies.

It is estimated that approximately 25 to 41 subjects will be enrolled into Phase 1 (dose escalation) of the study. The number of subjects is dependent on the tested dose cohorts and safety profile of AFM24.

Additionally, 3 expansion cohorts (in Phase 2a [Expansion Phase]), with up to a total of 39, 41, and 41 subjects in Cohorts A, B, and C, respectively, for a maximum of 121 subjects, will be enrolled to assess the preliminary efficacy of AFM24 in 3 different subject populations. Depending on the preliminary efficacy observed in the dose escalation phase (Phase 1) of the study, additional expansion cohorts may be added by a protocol amendment.

3.11 Study Initiation and Completion

The start of this clinical study is defined as the first act of screening (signing of the Main ICF) for a potential subject.

The end of the study is defined as when all subjects have completed the first Long-term Follow-Up interval, withdrawn, or died, whichever occurs first.

4.0 SELECTION AND WITHDRAWAL OF SUBJECTS

Subjects will be considered eligible to be enrolled in the study if ALL the inclusion criteria and NONE of the exclusion criteria are met as defined below.

Prospective approval of protocol deviations to recruitment and enrollment criteria, also known as protocol waivers or exemptions, is not permitted. Please note that based on various guidelines (eg, *NCCN Guidelines: Cancer and COVID-19 Vaccination* [NCCN 2021] and *MHRA Guidance on Coronavirus [COVID-19]* [MHRA 2021]), COVID-19 vaccination should be prioritized for subjects with cancer with the understanding that there are limited safety and efficacy data in this subject group. These guidelines also state:

- “Delay of vaccination until immunosuppressive therapy is reduced and/or based on immunophenotyping of T cell and B cell immunity can be considered.”
- “Systemic corticosteroids and targeted agents are expected to blunt immune responses to vaccination.”

This study utilizes a mandatory premedication regimen that contains corticosteroids for at least the duration of the first cycle (ie, Cycle 1). **Therefore, for any new subjects to be enrolled in the study**, every effort should be made to vaccinate subjects prior to being considered for this study based on the Investigator’s risk/benefit analysis for each subject. Any COVID-19 vaccination should be at least 2 weeks prior to C1D1; live attenuated vaccines at least 4 weeks prior to C1D1. **For subjects whose opportunity for COVID-19 vaccination arrives during the conduct of the study (ie, ongoing subjects in the study)**, see instructions for COVID-19 vaccination provided in Section 5.6.1.1.

